9.7.3 Secondary Efficacy Variables

9.7.3.1 Factor VIII Replacement Therapy/Bleeding Episodes

Secondary efficacy variables include:

- Change in the annualized utilization (IU/kg/year) and infusion (number/year) rates of exogenous FVIII replacement therapy during Week 5 to Week 52 post-BMN 270 infusion from the baseline number and utilization of exogenous FVIII replacement therapy, for subjects receiving FVIII prophylaxis during the 12 months prior to study entry, or change in administration of exogenous FVIII replacement therapy Week 27 to Week 52 post-BMN 270 infusion for subjects receiving prior emicizumab prophylaxis.
- Change in the annualized number of bleeding episodes requiring exogenous FVIII replacement treatment (annualized bleeding rate, ABR) during Week 5 to Week 52 post-BMN 270 infusion for subjects receiving prior FVIII prophylaxis, or Week 27 to Week 52 post-BMN 270 infusion for subjects receiving prior emicizumab prophylaxis, from the baseline ABR during the 12 months prior to study entry.

Subjects must have high quality documented historical data available concerning previous bleeding episodes and hemophilia treatment over the previous 12 months in order to be eligible to enroll in the study. During the study, subjects will be asked at each study visit to

report the use of factor replacement therapy and the number of bleeding episodes since the previous visit. This information will be captured on the subject's diary or other subject records.

Subjects are strongly encouraged to immediately consult Investigator for guidance regarding exogenous FVIII administration for suspected bleeds or bleeding episodes within the first 30 days post-BMN 270 infusion.

In subjects who experience recurrent bleeding episodes, the Investigator and Medical Monitor will discuss whether to resume prior FVIII prophylaxis or use of emicizumab.

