Treatment of severe HA includes intravenous injection of plasma-derived or recombinant human FVIII protein (rhFVIII) concentrates, both as prophylaxis 2-3 times per week, and at the time of a bleed, to prevent or control bleeding episodes, respectively and/or subcutaneous injection of a bi-specific monoclonal antibody, emicizumab, as prophylaxis 1-4 times per month. The half-life for FVIII (12 to 18 hours for most approved products) necessitates frequent infusions, and although a major advance in the treatment of HA, it remains common for severe HA patients to continue to have multiple bleeding events on prophylactic therapy (median annualized bleeding rate [ABR] of 1-4 with prophylaxis treatment in a recently published retrospective observational study and between 1-2 in 6 prospective FVIII interventional studies) and on-demand-only therapy (median ABR of 4.5-18 in a recently published retrospective study and between 20-60 in		

NAME OF COMPANY	SUMMARY TABLE	FOR NATIONAL AUTHORITY USE ONLY:
BioMarin Pharmaceutical Inc. [name]	Referring to Part of the Dossier:	
NAME OF FINISHED PRODUCT: BMN 270	Volume:	
NAME OF ACTIVE INGREDIENT: AAV5-hFVIII-SQ	Page:	

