
6 prospective FVIII interventional studies). The consequence of multiple bleeding events is the development of debilitating multiple-joint arthropathy and substantially increased risk of death. Chemical modification (eg, direct conjugation of polyethylene glycol (PEG) polymers) and bioengineering of FVIII (eg, FVIII-Fc fusion proteins) improve half-life by approximately 50%, and thus, show promise in reduced dosing and maintaining activity levels above a 1% trough for a greater proportion of the dosing interval. However, patients with severe HA who are treated with extended half-life FVIII remain dependent on multiple infusions to maintain critical levels of FVIII activity. While emicizumab prophylaxis has yielded lower bleed rates compared to prior FVIII prophylaxis, it does not physiologically recapitulate the coagulation system, requires chronic, life-long therapy, and still necessitates the use of on-demand FVIII concentrates for treatment of breakthrough bleeds. There is therefore a strong unmet need for a fully preventive treatment of HA to give patients a FVIII level compatible with a normal and hemorrhage-free life.
 
Gene therapy offers the potential of disease-modifying therapy by continuous endogenous production of active FVIII following a single intravenous infusion of a vector encoding the appropriate gene sequence for long-term episomal expression. HA is well-suited for a gene replacement approach because clinical manifestations are attributable to the lack of a single gene product (FVIII) that circulates in minute amounts (200 ng/ml) in the plasma. Tightly regulated control of gene expression is not essential, and even modest increases in the level of FVIII (any increase of the plasma level by 2 ng/ml induces an increase in activity of 1%) can ameliorate the severe form of hemophilia A. Thus, relatively small changes in endogenous FVIII activity can result in clinically relevant improvements in disease phenotype. Finally, the circulating FVIII response to gene transduction can be assessed using validated quantitative rather than qualitative endpoints that are easily assayed using established laboratory techniques.
 
Several different gene transfer strategies for FVIII replacement have been evaluated, but adeno-associated viral (AAV) vectors show the greatest promise. They have an excellent and well-defined safety profile, and can direct long-term transgene expression with tropism and promoter specificity for specific tissues, such as the liver (for serotypes 2, 5 and 8 among others). Indeed, an ongoing gene therapy clinical trial for a related disorder, hemophilia B, has established that stable (median follow-up of 6.7 years) expression of human factor IX (hFIX) at levels that are sufficient for conversion of their bleeding phenotype from severe to moderate or mild is achievable following a single peripheral vein infusion of AAV8-hFIX vector. Several participants in this trial have been able to discontinue factor prophylaxis without suffering spontaneous hemorrhages, even when they undertook activities that previously resulted in bleeding. Thus, gene therapy treatment has resulted in a substantial improvement in their quality of life.
 
BMN 270 is an AAV5-based gene therapy vector that expresses the SQ form of hFVIII under the control of a hybrid human liver-specific promoter (Figure 1).
		

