
 Assess the impact of BMN 270 with prophylactic corticosteroids on the use of exogenous FVIII replacement therapy from Week 5 to Week 52 for subjects receiving prior FVIII prophylaxis or on use of emicizumab from Week 27 to Week 52 for subjects receiving prior emicizumab prophylaxis Assess the impact of BMN 270 with prophylactic corticosteroids on the number of bleeding episodes requiring exogenous FVIII replacement therapy from Week 5 to Week 52 for subjects receiving prior FVIII prophylaxis or on use of emicizumab from Week 27 to Week 52 for subjects receiving prior emicizumab prophylaxis Assess the impact of BMN 270 with prophylactic corticosteroids on quality of life as measured by the Haemo-QoL-A questionnaire at Week 52 of the study compared to baseline 		

NAME OF COMPANY	SUMMARY TABLE	FOR NATIONAL AUTHORITY USE ONLY:
BioMarin Pharmaceutical Inc. [name]	Referring to Part of the Dossier: Volume:	
NAME OF FINISHED PRODUCT: BMN 270	Page:	
NAME OF ACTIVE INGREDIENT: AAV5-hFVIII-SQ	Reference:	

The tertiary efficacy objective of the study is to:
 
 Assess the impact of BMN 270 with prophylactic corticosteroids on patient-reported outcomes (PROs) (other than Haemo-QoL-A) at Week 52 of the study compared to baseline 		

The exploratory efficacy objective of the study is to:
 
 Assess the efficacy of BMN 270 with prophylactic corticosteroids defined as FVIII activity, as measured by chromogenic substrate assay, during Weeks 49-52, following intravenous infusion of BMN 270 for subjects with detectable AAV5 total antibodies below the minimum required dilution at Screening 		

The safety objectives of the study are to:
 
 Evaluate the safety of BMN 270 with prophylactic corticosteroids during the first 52 weeks following intravenous infusion of BMN 270 Assess the long-term safety of BMN 270 with prophylactic corticosteroids 		

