
 1. Any condition that, in the opinion of the Investigator or a hepatologist or radiologist, would make liver biopsy contraindicated. This includes (but is not limited to): abnormalities detected on liver ultrasound performed within 28 days of procedure or prior liver ultrasound result within 90 days that would preclude safe performance of the biopsy. 		

NAME OF COMPANY	SUMMARY TABLE	FOR NATIONAL AUTHORITY USE ONLY:
BioMarin Pharmaceutical Inc. [name]	Referring to Part of the Dossier: Volume:	
NAME OF FINISHED PRODUCT: BMN 270	Page:	
NAME OF ACTIVE INGREDIENT: AAV5-hFVIII-SQ	Reference:	
INVESTIGATIONAL PRODUCT(S), DOSE, ROUTE AND REGIMEN: Each subject will receive a single intravenous infusion of BMN 270 at 6E13 vg/kg. The volume of infusion will depend on the subject's weight		
REFERENCE THERAPY(IES), DOSE, ROUTE AND REGIMEN: No reference therapy will be evaluated in this study.		
DURATION OF TREATMENT: BMN 270 is given as a single dose by intravenous infusion.		
CRITERIA FOR EVALUATION: Efficacy: Primary efficacy endpoint: 
 Change of the hFVIII activity, as measured by chromogenic substrate assay, during Weeks 49-52 post-BMN 270 infusion from baseline. Each subject's hFVIII activity during Weeks 49-52 is defined as the median of the values obtained during this 4-week window. Values for hFVIII activity will be excluded if obtained within 72 hours since the last infusion of exogenous FVIII protein concentrates. Secondary efficacy endpoints: 
 Change from baseline in the annualized utilization (IU/kg/year) and infusion rate (number/year) of exogenous FVIII replacement therapy during Week 5 to Week 52 post-BMN 270 infusion, for subjects receiving FVIII prophylaxis during the 12 months prior to study entry or change from baseline in the annualized utilization (mg/kg/year) of emicizumab during Week 27 to Week 52 post-BMN 270 infusion for subjects receiving prior emicizumab prophylaxis. Change from baseline in the annualized number of bleeding episodes requiring exogenous FVIII replacement treatment (annualized bleeding rate, ABR) during Week 5 to Week 52 post-BMN 270 infusion for subjects receiving prior FVIII prophylaxis, or Week 27 to Week 52 post-BMN 270 infusion for subjects receiving prior emicizumab prophylaxis Change from baseline in the total score of Haemo-QoL-A at Week 52 post-BMN 270 infusion 		

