9.1 Overall Study Design and Plan

This is a Phase 3b, single arm, open-label study in hemophilia A patients with residual FVIII levels ≤ 1 IU/dL. Subjects will be enrolled at approximately 10 sites worldwide. Subjects must have high-quality, well-documented historical data available concerning previous bleeding episodes and exogenous FVIII usage over the previous 12 months in order to be eligible to enroll in the study.

Approximately 20 adult subjects with severe HA will receive a 6E13 vg/kg dose of BMN 270 as a single intravenous infusion in conjunction with receipt of a 19-week prophylactic corticosteroid regimen starting on the day of the BMN 270 infusion.

Post-infusion, subjects will be eligible to receive on-demand corticosteroids, as indicated. (Figure 9.1.1).

Figure 9.1.1: 270-303 Study Schema

In order to minimize bias in the ongoing study and to assure safe and ethical conduct of the clinical trial, an independent Data Monitoring Committee (DMC), consisting of experts in clinical trials, statistics, and hemophilia, will be convened. The DMC will have access during the trial to amalgamated FVIII activity levels, FVIII usage, and bleeding data and review available safety and efficacy (eg, FVIII activity) data during the study on an ongoing basis; they may determine, based on emerging data and the risk/benefit profile, that further enrollment should be paused to enable modification of the protocol or discontinued.

The final analysis for the study will be performed after all subjects have been followed for 52 weeks post-BMN 270 infusion (or have discontinued study participation prior to Week 52). After the final analysis, safety and efficacy will then continue to be assessed long-term for a total of approximately 5 years for each subject.

To avoid breakthrough bleeding, subjects will only discontinue exogenous prophylactic FVIII replacement therapy 4 weeks following infusion of BMN 270 or if FVIII activity has consistently increased above 5 IU/dL, whichever is earlier. Four weeks represents the time by which endogenous production of FVIII following gene transfer is expected to be efficacious, based on prior study results. Subjects previously receiving emicizumab, given its approximate 1-month half-life, will remain on emicizumab prophylaxis until BMN 270 infusion, with their final dose administered prior to Day 1.

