9.4.8.1 Concomitant Hemophilia Treatments

To avoid breakthrough bleeding, subjects will only discontinue exogenous prophylactic FVIII replacement therapy 4 weeks following infusion of BMN 270 or if FVIII activity has consistently increased above 5 IU/dL, whichever is earlier. Subjects previously receiving emicizumab, given its approximate 1-month half-life, will remain on emicizumab prophylaxis until BMN 270 infusion, with their final dose administered prior to Day 1.

FVIII replacement therapy can always be taken as needed by the subject for treatment of an acute bleeding episode; the subject must carefully record his treatment and bleeding episodes in his diary. Prophylactic FVIII use can be used on a case-by-case basis and in consultation with the Medical Monitor to prevent bleeding in extenuating circumstances (eg peri-operative).

In addition, information on FVIII usage and bleeding episodes by medical history must be well-documented and available and will be collected from subjects for the 12-month period immediately preceding study enrollment. Further information on the details that should be provided as part of the subject's well-documented medical and FVIII usage history are provided in the Investigator Site File Binder.

In order to enable rigorous comparisons of pre-study versus on-study FVIII usage and bleeding episodes, the Medical Monitor will review each screened patient's prior bleed and hemophilia medication logs to determine if they are of "high-quality". Elements that will be

assessed to judge the quality of such historical data may include, but are not limited to, the following:

- Date, type (eg, joint, muscle, other), location of bleeds
- Date, name, dose (calculated in IU/kg), and reason for use (eg, usual prophylaxis, one-time prophylaxis, treatment for bleed, surgery) of hemophilia medications.

9.4.8.2 Therapeutic Corticosteroid Treatment and/or Alternative Immunosuppressive Agent Treatment of Elevated Hepatic Transaminases

Prior to dosing, all subjects must be screened per steroid prescription guidelines to ensure the subject is eligible to receive corticosteroid treatment as outlined in the protocol. Refer to corticosteroid prescription guidelines for recommended monitoring for, and management of, potential side effects of corticosteroids, including guidance on medications that should be avoided during corticosteroid treatment.

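### For prior-emicizumab subjects, the Weeks 27-52 therapy-use endpoint is emicizumab in the Synopsis and objectives but exogenous FVIII in Section 9.7.3.1

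*Protocol*

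**What the plan says.** All references are to Protocol Amendment 1 unless stated.

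- **Objectives** (Synopsis and Section 8): the therapy-use objective for this group is the impact "on use of emicizumab from Week 27 to Week 52 for subjects receiving prior emicizumab prophylaxis".
- **Synopsis, secondary endpoints and analysis text**: the measure is change from baseline in "annualized utilization (mg/kg/year) of emicizumab during Week 27 to Week 52 post-BMN 270 infusion for subjects receiving prior emicizumab prophylaxis". The analysis text repeats this emicizumab measure in the bullet on infusion rate, so no infusion rate is defined there for these subjects.
- **Section 9.7.3.1**: the variable is "change in administration of exogenous FVIII replacement therapy Week 27 to Week 52 post-BMN 270 infusion for subjects receiving prior emicizumab prophylaxis". No unit is attached for this group.
- **Section 9.1**, on stopping emicizumab: these subjects "will remain on emicizumab prophylaxis until BMN 270 infusion, with their final dose administered prior to Day 1".
- **Section 9.4.8.1**, on FVIII after infusion: "FVIII replacement therapy can always be taken as needed by the subject for treatment of an acute bleeding episode". Also: "Prophylactic FVIII use can be used on a case-by-case basis and in consultation with the Medical Monitor to prevent bleeding in extenuating circumstances", where the example given is peri-operative use.
- **Recurrent bleeding**: the Synopsis design text and Section 9.1 have the investigator and Medical Monitor discuss resuming earlier FVIII prophylaxis. Section 9.7.3.1 adds emicizumab to that discussion.

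**The concern.** Population and window are the same in both definitions, but the drug being counted is not. This is a contradiction inside the current text, and the original protocol has the same one, so the amendment carried it forward. An analysis plan could choose either version, but it would then contradict another part of the protocol.

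Adopting one version as it stands would not be enough. The endpoint is meant to show how far gene transfer frees subjects from other haemophilia therapy. After infusion these subjects may use FVIII, and under Section 9.7.3.1 a return to emicizumab is also contemplated. Each definition sees only one of the two. In an open-label, single-arm study, the choice between them should not be left until results are visible.

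**Working it through.** The plan states no figure for this endpoint, so there is none to reproduce. The check is a comparison of the two definitions.

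**Notation.** E0 is baseline emicizumab use per year and F0 is baseline FVIII use per year. F0 is on-demand use, because the Synopsis rationale says emicizumab "still necessitates the use of on-demand FVIII concentrates for treatment of breakthrough bleeds"; its size is not given. F1 is annualized FVIII use in Weeks 27-52. The change is the absolute change from baseline, as the plan specifies.

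| Subject in Weeks 27-52 | Synopsis (emicizumab) | Section 9.7.3.1 (FVIII) |
|---|---|---|
| No emicizumab, no FVIII | 0 - E0 = -E0 | 0 - F0 = -F0 |
| No emicizumab, some FVIII | 0 - E0 = -E0 | F1 - F0 |
| Back on emicizumab at baseline dose all window, no FVIII | E0 - E0 = 0 | 0 - F0 = -F0 |

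The Synopsis column cannot separate the first two rows, and the Section 9.7.3.1 column cannot separate the first and third. For a subject in the second row with F1 above F0, the two definitions move in opposite directions.

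**Scale of what the Synopsis version omits.** Weeks 27-52 are 26 weeks, so the annualization factor is 52/26 = 2. Section 9.7.3.1 gives no unit here; infusions per year are assumed.

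- On-demand use: one infusion in the window counts as 1 x 2 = 2 per year. With 1 to 4 infusions (assumed), F1 is 2 to 8 per year.
- Hypothetical extreme, FVIII prophylaxis for the whole window: the Synopsis rationale describes FVIII "both as prophylaxis 2-3 times per week". Then 26 x 2 = 52 to 26 x 3 = 78 infusions, or 104 to 156 per year.
- The same for half the window (13 weeks): 26 to 39 infusions, or 52 to 78 per year.

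In every case the Synopsis measure stays at -E0, provided emicizumab is not restarted.

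**Weight of one subject.** The split by prior therapy is not stated. If the group had 2, 4 or 8 subjects (assumed), one subject would carry 1/2 = 50%, 1/4 = 25% or 1/8 = 12.5% of the group mean.

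**The case against.** The best defence is that this is a drafting slip in one place. The objectives, the Synopsis endpoints and the Synopsis analysis text agree on emicizumab, as does Section 14.3 of the original protocol; only Section 9.7.3.1 departs. (Section 14.3 of Amendment 1 is not in the text at hand.) On this view, aligning Section 9.7.3.1 with the rest ends the matter. A measure that falls to zero when prior prophylaxis stops is also no flaw in itself: prior-FVIII subjects stop prophylaxis too, and the endpoint shows whether the old regimen stayed off. On-demand FVIII feeds the bleeding-rate endpoint for the same subjects and window, and lost expression would show in FVIII activity.

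Much of this stands and keeps the point small, but it does not remove the contradiction. Simple alignment would delete the only definition that counts FVIII in this group. Bleeding rate counts treated bleeds, not the amount of product used, and prophylaxis that works lowers it.

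A reader might infer more than the documents support:

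- **That the Synopsis endpoint would credit a subject on long-term FVIII prophylaxis with a 100% reduction.** The plan specifies a mean absolute change, not a percentage. Section 9.4.8.1 confines prophylactic FVIII to extenuating circumstances. The treatment-failure definition in Section 9.1 does refer to dependence on prophylactic FVIII without limiting this to prior-FVIII subjects, so such use is not ruled out. Even so, no passage expressly plans maintenance FVIII for this group.
- **That the Synopsis and Section 9.1 leave these subjects no rescue option.** They describe a discussion, not an exclusive list. Emicizumab is not among the prohibited medications in Section 9.4.8, and Section 9.7.3.1 names it.

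**Conclusion.** The contradiction is real and needs correcting before the 52-week analysis. For prior-emicizumab subjects, the reported change in therapy use depends on which section is followed, and each definition misses one kind of therapy that the protocol allows for.

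The point is minor. It concerns one descriptive secondary endpoint in a subgroup of unstated size. The primary endpoint, its test and the power calculation do not depend on it, and bleeding rate and FVIII activity partly cover what is missed. The comparison of definitions needs no assumed number. The on-demand range, the group sizes and the 104 to 156 infusions per year are illustrations only. How many of these subjects will use FVIII or restart emicizumab cannot be known from the protocol.

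**What to change.** Use one definition in the Synopsis objectives, endpoints and analysis text, Section 8 and Section 9.7.3.1, and check that Section 14.3 matches. For prior-emicizumab subjects in Weeks 27-52, report change from baseline in both:

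- emicizumab, in mg/kg/year;
- exogenous FVIII, in IU/kg/year and infusions per year.

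Align the wording on resuming prophylaxis in the Synopsis design text and Section 9.1 with Section 9.7.3.1, so that both agents are named. A count of subjects who restarted any prophylaxis by Week 52 would be a useful addition but is optional.

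No new data are needed. Entry requires 12 months of documented haemophilia therapy (Section 9.3.1), medications added during the study go on the case report form (Section 9.4.8), and FVIII use is asked about at each visit (Section 9.7.3.1). The cost is the rewording, a few extra descriptive lines, and a summary that may look less favourable than one counting emicizumab alone.

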14.3 Secondary Efficacy Endpoints

The analyses of the secondary efficacy endpoints will be descriptive. Mean and associated 95% confidence interval will be provided for the following secondary endpoints, where the baseline value will be derived from the data in the approximately 12-month period prior to BMN 270 infusion:

- Change from baseline in the annualized utilization (IU/kg/year) of exogenous FVIII replacement therapy during Weeks 5-52 post-BMN 270 infusion, for subjects receiving FVIII prophylaxis during the 12 months prior to study entry, or change from baseline in the annualized utilization (mg/kg/year) of emicizumab during Week 27 to Week 52 post-BMN 270 infusion for subjects receiving prior emicizumab prophylaxis
- Change from baseline in the annualized infusion rate (number/year) of exogenous FVIII replacement therapy during Weeks 5-52 post-BMN 270 infusion, for subjects receiving FVIII prophylaxis during the 12 months prior to study entry, or change from baseline in the annualized utilization (mg/kg/year) of emicizumab during Week 27 to Week 52 post-BMN 270 infusion for subjects receiving prior emicizumab prophylaxis
- Change from baseline in the annualized number of bleeding episodes (number/year) requiring exogenous FVIII replacement treatment during Weeks 5-52 post-BMN 270 infusion for subjects receiving prior FVIII prophylaxis, or Weeks 27-52 post-BMN 270 infusion for subjects receiving prior emicizumab prophylaxis

Mean change from baseline and associated 95% confidence interval will be calculated for the total score of Haemo-QoL-A at Week 52 post-BMN 270 infusion as well.

The missing value of the change for annualized utilization and annualized infusion rate will be imputed as 0. The missing value of the change for annualized number of bleeding episodes will be imputed using the median value of the changes of all observed cases.

A sensitivity analysis is planned to analyze ABR using a generalized linear mixed model assuming negative binomial as the underlying distribution. The model will include period (pre- to post-BMN 270 infusion) as the only factor, repeated within subject. The actual number of bleeding episodes will be used as the dependent variable with the time period adjustment (annualization) being implemented as the offset.

To assess the impact of missing data, analyses using observed case are planned as sensitivity analyses for the secondary endpoints. Multiple imputation methods may also be performed.

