
 • Change from baseline in the annualized utilization (IU/kg/year) of exogenous FVIII replacement therapy during Weeks 5-52 post-BMN 270 infusion, for subjects receiving FVIII prophylaxis during the 12 months prior to study entry, or change from baseline in the annualized utilization (mg/kg/year) of emicizumab during Week 27 to Week 52 post-BMN 270 infusion for subjects receiving prior emicizumab prophylaxis • Change from baseline in the annualized infusion rate (number/year) of exogenous FVIII replacement therapy during Weeks 5-52 post-BMN 270 infusion, for subjects receiving FVIII prophylaxis during the 12 months prior to study entry, or change from baseline in the annualized utilization (mg/kg/year) of emicizumab during Week 27 to Week 52 post-BMN 270 infusion for subjects receiving prior emicizumab prophylaxis • Change from baseline in the annualized number of bleeding episodes (number/year) requiring exogenous FVIII replacement treatment during Weeks 5-52 post-BMN 270 infusion for subjects receiving prior FVIII prophylaxis, or Weeks 27-52 post-BMN 270 infusion for subjects receiving prior emicizumab prophylaxis from baseline 		

Mean change from baseline and associated 95% confidence interval will be calculated for the total score of Haemo-QoL-A at Week 52 post-BMN 270 infusion as well.
		

The incidence of AEs will be summarized by system organ class, preferred term, relationship to study drug, seriousness, and severity. Clinical laboratory test values, vital signs, vector shedding and immune response parameters will be summarized descriptively by visit.
		

The final analysis for the study will be performed after all subjects have been followed for 52 weeks post-BMN 270 infusion (or have discontinued study participation prior to Week 52). No formal interim analysis is planned. Informal analyses (ie, no hypothesis testing) may be performed at different timepoints to assess efficacy and safety over time. The primary efficacy endpoint for such analyses involves hFVIII activity, as measured by chromogenic substrate assay, and is defined as median FVIII activity during a specific 4-week time interval post-BMN 270 infusion.
		

Details of the planned analyses will be specified in the SAP.
		

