In subjects who experience recurring bleeding episodes, the Investigator and Medical Monitor will discuss whether to resume prior FVIII prophylaxis. Subjects who do not respond to BMN 270 treatment (ie, treatment failure, manifesting as either failure to achieve FVIII activity \geq 5 IU/dL by Week 52 or inability to maintain independence from prophylactic FVIII replacement therapy due to joint bleeding episodes, in the judgment of the Investigator) may, at the Investigator's discretion and after discussion with the Medical Monitor or Sponsor-designated Data Monitor, follow an abbreviated visit schedule after Week 52 of the study by attending only the Q12W and End of Year visits during Years 2-5. Subjects who are not attending the Q4W/Q6W visits during Years 2-5 may receive a scheduled monthly follow-up telephone call from the site to ask about adverse events, concomitant medications, and bleeding events/FVIII replacement usage.

There will be an ongoing review of individual subject safety by the Medical Monitor, and both safety and efficacy data by the DMC. Patients will receive prophylactic corticosteroids with tapering of the dosage based upon consideration of ALT values, FVIII activity levels, and consultation with the Investigator and the Medical Monitor. Therapeutic oral corticosteroids may be initiated if a subject's ALT values increase from baseline levels, after consultation between the Investigator and the Medical Monitor.

In case of a safety concern, additional unscheduled laboratory tests may be performed locally (at the Investigator's discretion) in order to facilitate timely and appropriate clinical management decisions; where possible, a matched sample for testing at the central laboratory should be collected (using the Unscheduled Visit lab kit) at the same time as the local unscheduled sample.

Any safety signal may trigger a review of the data and possible additional immunogenicity studies or other diagnostics deemed necessary that include an assessment of cellular immune responses using collected peripheral blood mononuclear cells (PBMCs).

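### The bleeding-rate endpoint counts time after prophylaxis is resumed, which masks worsening in subjects who fail BMN 270

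*Protocol*

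**What the plan says.** **Return to prophylaxis.** Section 9.7.3.1 states: "In subjects who experience recurrent bleeding episodes, the Investigator and Medical Monitor will discuss whether to resume prior FVIII prophylaxis or use of emicizumab". Section 9.1 covers the same situation without naming emicizumab: "In subjects who experience recurring bleeding episodes, the Investigator and Medical Monitor will discuss whether to resume prior FVIII prophylaxis". Section 9.1 also lists, as one form of treatment failure, "inability to maintain independence from prophylactic FVIII replacement therapy due to joint bleeding episodes", in the investigator's judgment. The reduced visit schedule for such subjects begins only after Week 52. Emicizumab is not among the prohibited medications in Section 9.4.8.

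**Bleeding endpoint.** Under the Synopsis (Analysis), treated bleeds are counted "during Weeks 5-52 post-BMN 270 infusion for subjects receiving prior FVIII prophylaxis, or Weeks 27-52 post-BMN 270 infusion for subjects receiving prior emicizumab prophylaxis". The primary efficacy population (mITT) is every infused AAV5-antibody-negative subject. For the ABR sensitivity model, Section 14.3 says: "The model will include period (pre- to post-BMN 270 infusion) as the only factor, repeated within subject". The actual count is the outcome and observation time is the offset. The imputation rules in Section 14.3 apply to missing changes only. All secondary analyses are descriptive.

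**Background rates (Synopsis, Study Rationale).** The retrospective study gives a "median annualized bleeding rate [ABR] of 1-4 with prophylaxis treatment"; the prospective studies give 1-2. On-demand medians are 4.5-18 (retrospective) and 20-60 (prospective).

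Section 14.3 can be read only in the original protocol, because the supplied Amendment 1 text ends before its Section 14. The Amendment 1 Synopsis has the same windows and populations, and the amendment summary lists no statistical change.

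**The concern.** Section 8 sets the objective as the impact of BMN 270 on treated bleeds. Elsewhere the protocol keeps exogenous treatment out of its efficacy measures. FVIII prophylaxis stops by 4 weeks and bleed counting starts at Week 5. Prior emicizumab users, whose drug has a half-life of about a month, are counted only from Week 27. The primary endpoint drops activity values within 72 hours of an FVIII infusion. Nothing comparable applies once prophylaxis is resumed.

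Those who resume are selected for recurrent bleeding. Their later, protected weeks enter the ABR as if they were time on BMN 270 alone. Section 9.2 of Amendment 1 rules out a control group, so the pre/post change is the trial's evidence on bleeding.

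The companion endpoints show part of this. Resumed FVIII raises FVIII utilization and infusion rate. Emicizumab started by a prior-FVIII subject, if Section 9.7.3.1 allows it, enters no utilization endpoint, because emicizumab use is measured only in prior emicizumab users. The bleeding effect could also be larger there, given the Synopsis statement: "While emicizumab prophylaxis has yielded lower bleed rates compared to prior FVIII prophylaxis".

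**Working it through.** The protocol gives no design figure for ABR. Its one calculated figure is 85% power for the primary endpoint with 16 subjects, effect size 0.8 and one-sided 0.025. This reproduces at 84.8% (noncentral t, 15 df, noncentrality 0.8 × √16 = 3.2) and is not affected by this point.

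**Inputs.**
- From the protocol: 16 mITT subjects; a 48-week window (Weeks 5-52); off-prophylaxis ABR *f* of 4.5, 18, 20 or 60.
- Assumed: one prior-FVIII subject resumes at Week 28, so Weeks 28-52 (25 weeks) are on prophylaxis and 23 are off; ABR on prophylaxis *p* = 2, inside the cited 1-4.

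**Formulas.** Recorded ABR = (23*f* + 25*p*)/48. Understatement for the subject = (25/48)(*f* − *p*) = 0.52(*f* − 2). Understatement of the mean = that value/16.

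| *f* | Recorded ABR | Subject understated by | Mean understated by |
|---|---|---|---|
| 4.5 | 3.2 | 1.3 | 0.08 |
| 18 | 9.7 | 8.3 | 0.52 |
| 20 | 10.6 | 9.4 | 0.59 |
| 60 | 29.8 | 30.2 | 1.9 |

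**What the dilution does.** With a baseline ABR of 2 and *f* = 20, the subject's true worsening of +18 is recorded as 10.6 − 2 = +8.6. With *f* = 4.5, +2.5 is recorded as +1.2. The worsening shrinks but does not become an improvement.

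**Dependence on *p*.** This matters at the low end. At *f* = 4.5 the shift in the mean is 0.52 × 0.5/16 = 0.02 for *p* = 4 and 0.52 × 3.5/16 = 0.11 for *p* = 1.

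**More resumptions, earlier.** Assume 2 of 16 resume after Week 16 (12 weeks off, 36 on), the other 14 have ABR 0.5, and baseline is 2.
- *f* = 20: recorded ABR of each is (12 × 20 + 36 × 2)/48 = 6.5. The mean is (14 × 0.5 + 2 × 6.5)/16 = 1.25, a change of −0.75. With *f* carried to Week 52 it is (7 + 40)/16 = 2.94, a change of +0.94.
- *f* = 4.5: the changes are −1.23 and −1.00.

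**Prior emicizumab users.** If such a subject resumes before Week 27, the whole window is on prophylaxis and the mean is understated by (*f* − 2)/16: 0.16 at 4.5 and 1.1 at 20. The bleeds that led to resumption then fall outside the window.

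**The case against.** The strongest reply is that counting every treated bleed in every infused subject is a legitimate treatment-policy choice, and that handling of later events can be left to the SAP, which is not shown. The first part stands, which is why the planned ABR should stay. The second stands only in part: Section 14.3 itself fixes the window, the imputation, the sensitivity model and its only factor.

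Other limits also stand. Every subject was on prophylaxis at baseline, so returning to the same prophylaxis pulls the change towards zero and creates no reduction. Resumed FVIII is visible in the utilization endpoints. The on-demand rates come from patients without gene transfer, and a subject with residual expression may bleed less.

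A reader might infer that a failing subject moved to emicizumab looks like a full responder on both bleeding and FVIII use. The documents do not support that. In the Week 28 example, bleeds and FVIII use over 23 of 48 weeks still count. The switch itself rests on an ambiguous sentence: in Section 9.7.3.1, resuming may govern both drugs, meaning a return to whichever the subject had before, and Section 9.1 names only FVIII.

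Nor is every resumption a treatment failure as Section 9.1 describes it. That description requires joint bleeding and the investigator's judgment, while Section 9.7.3.1 requires only recurrent bleeding.

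**Conclusion.** The point holds as a bias in a descriptive secondary endpoint. For subjects who resume continuous prophylaxis inside the window, the ABR mixes two treatments and masks worsening, and the mean change moves in BMN 270's favour. Per resuming subject in 16, the illustration gives about 0.1-0.5 bleeds per year at the retrospective on-demand rates and 0.6-1.9 at the prospective ones. It assumes resumption at Week 28 and ABR 2 on prophylaxis.

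The resumption frequency is unknown, so the actual bias could be negligible or material. The reversal of sign with two resumptions shows what is possible under chosen inputs and is not a forecast. The primary endpoint, type I error and power are unaffected.

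**What to change.** Keep the planned ABR and add to Section 14.3:

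- **(a)** A pre-specified ABR from Week 5 or 27 up to the start of any continuous prophylaxis (FVIII or emicizumab), with the observed time as the offset in the negative binomial model. Define continuous prophylaxis so that single peri-procedural doses do not count.
- **(b)** The number, timing and agent of resumptions.
- **(c)** A sensitivity analysis that assigns time on resumed prophylaxis an off-prophylaxis rate, such as the subject's own rate before resumption, with the protocol's cited on-demand ranges as bounds.

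Analysis (a) stops because of bleeding, so it should stand beside the planned ABR and not replace it. A prior emicizumab user who resumes before Week 27 contributes no time to (a) and must be covered by (b) and (c).

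Report emicizumab use in all subjects, whatever their prior therapy. Scoring a subject's FVIII-use change as zero from the date of a switch would not work, because the endpoint has one change value per subject for the whole window.

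Two contradictions must be reconciled by the sponsor: Sections 9.1 and 9.7.3.1 on whether emicizumab may be used after recurrent bleeding; and the Synopsis and Section 14.3 (emicizumab utilization) against Section 9.7.3.1 (FVIII administration) on which drug is measured in prior emicizumab users.

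Bleeds, FVIII use and concomitant medications are already collected. The cost is a little more analysis and possibly a smaller reported ABR benefit.
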